#### Secondary Endpoint

The secondary endpoints are:

- Safety and tolerability based on assessment of AEs, clinical laboratory assessments, 12-lead ECGs and vital signs.
- The hospital admission rate 28 days after treatment initiation.
- Incidence of complications associated with influenza after the start of study treatment:
  - Pulmonary complications:

The pulmonary complications of influenza include respiratory failure, primary viral pneumonia, secondary bacterial pneumonia (including pneumonia attributable to unusual pathogens), exacerbations of chronic underlying pulmonary diseases such as COPD, asthma, and bronchitis.

- Respiratory failure: defined as either hypoxemic respiratory failure characterized by an arterial oxygen tension (PaO2) lower than 60 mmHg with a normal or low arterial carbon dioxide tension (PaCO2), or hypercapnic respiratory failure characterized by a PaCO2 higher than 50 mmHg.
- Primary viral pneumonia: a progressive event involving the lower respiratory tract with bilateral and/or diffuse radiological findings. No bacterial agent is identified using sputum cultures.
- Secondary bacterial pneumonia (including pneumonia attributable to unusual pathogens): a clinical event compatible with lower respiratory tract involvement, with lobar infiltrates on radiological studies and/or microbiological isolate of a bacterial pathogen, including unusual pathogens.
- Exacerbations of chronic underlying pulmonary diseases such as COPD and asthma: subjects with documented medical history of COPD or asthma with a sudden worsening of symptoms and deteriorating respiratory function (the latter as evidenced by worsening hypoxia, tachypnea, etc.) The event must start before a full recovery from the influenza infection occurred.
- Bronchitis

- Extrapulmonary complications:
  - Cardiovascular and cerebrovascular disease (eg, myocardial infarction, congestive heart failure, arrhythmia, stroke)
  - Muscular disorders (eg, myositis, rhabdomyolysis)
  - Central nervous system (CNS) involvement
  - Acute exacerbation of chronic kidney disease
  - Severe dehydration
  - Decompensation of previously controlled diabetes mellitus
  - Other infections (eg, sinusitis, otitis)

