### 4.1. Inclusion Criteria

Each potential subject must satisfy all of the following criteria to be enrolled in the study:

1. Male or female, 13 to 85 years of age, inclusive. Note: Adolescent subjects (13 to 17 years) will be enrolled in selected countries and study sites consistent with local regulations.
2. Present to the clinic with symptoms suggestive of a diagnosis of acute influenza and have at least 1 respiratory symptom and at least 1 systemic symptom, both scored as at least “moderate” if the symptom did not pre-exist before influenza onset, or scored worse than usual if the symptom pre-existed as determined by subject’s ratings on Module 1 of the Flu-iiQ™ and the Pre-existing Symptom Questionnaire in the ePRO device. Symptoms must include the following by category:
  1. Respiratory symptoms: cough, sore throat, nasal congestion
  2. Systemic symptoms: headache, body aches or pain, feverishness, fatigue
3. Tested positive for influenza A infection after the onset of symptoms, using a rapid influenza diagnostic test (RIDT) or, if available, a PCR-based or other rapid molecular diagnostic assay.

4. Not be in need of hospitalized medical care at screening. Emergency room or hospital observation status for an anticipated duration of <24 hours is not considered hospitalization as long as a determination of the need for hospitalization has not been made.
5. Enrollment and initiation of study drug treatment  $\leq 72$  hours after onset of influenza symptoms.
6. Must sign an ICF/assent form (or their legally acceptable representative must sign) indicating that he or she understands the purpose of, and procedures required for, the study and is willing to participate in the study. Assent is also required of children capable of understanding the nature of the study, typically subjects 7 years of age and older. Subjects must sign a separate ICF/assent form if he or she agrees to provide an optional DNA sample for research (where local regulations permit). Refusal to give consent for the optional DNA research sample does not exclude a subject from participation in the study.
7. Before randomization, a woman must be either:
  - a. Not of childbearing potential defined as:
    - Premenarchal  
*A premenarchal state is one in which menarche has not yet occurred.*
    - Postmenopausal  

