#### 11.4. Efficacy Analyses

Descriptive statistics will be used for all efficacy endpoints and will be tabulated by treatment arm and stratification factors (baseline SOC and time since onset of symptoms).

Subgroup analyses will be performed by, but might not be limited to, region and age group.

As a confirmatory strategy, to account for multiplicity in the statistical evaluation of the most important efficacy endpoints, hierarchical testing will be applied to control for overall Type I error. The following endpoints are included in the confirmatory strategy:

1. Time to resolution of the 7 primary influenza-related symptoms (cough, sore throat, headache, nasal congestion, feeling feverish, body aches and pains, fatigue), ie, primary endpoint
2. Incidence of complications associated with influenza after the start of study treatment
3. Hospital admission rates 28 days after treatment initiation

First, the primary endpoint will be tested for superiority of pimodivir in combination with SOC over placebo in combination with SOC at the 2-sided 5% significance level. If superiority is shown on the primary endpoint, the first secondary endpoint in the sequence as indicated above

will be tested for superiority at the same significance level. If superiority is shown for this secondary endpoint, the second (and last) secondary endpoint in sequence will be tested. In case superiority is not shown for an endpoint, no further endpoints in the sequence will be tested for superiority.

For the primary endpoint, the results from the Gehan-Wilcoxon test will be used in the hypothesis testing. For the secondary endpoints, incidence of complications associated with influenza after the start of study treatment and hospital admission rates 28 days after treatment initiation, the results of the logistic regression will be used.

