##### **Serious Adverse Event**

An SAE event based on ICH and European Union Guidelines on Pharmacovigilance for Medicinal Products for Human Use is any untoward medical occurrence that at any dose:

- Results in death.
- Is life-threatening  
(The subject was at risk of death at the time of the event. It does not refer to an event that hypothetically might have caused death if it were more severe.).
- Requires inpatient hospitalization or prolongation of existing hospitalization.
- Results in persistent or significant disability/incapacity.

- Is a congenital anomaly/birth defect.
- Is a suspected transmission of any infectious agent via a medicinal product.
- Is Medically Important\*.

\*Medical and scientific judgment should be exercised in deciding whether expedited reporting is also appropriate in other situations, such as important medical events that may not be immediately life threatening or result in death or hospitalization but may jeopardize the subject or may require intervention to prevent one of the other outcomes listed in the definition above. These should usually be considered serious.

If a serious and unexpected AE occurs for which there is evidence suggesting a causal relationship between the study drug and the event (eg, death from anaphylaxis), the event must be reported as a serious and unexpected suspected adverse reaction even if it is a component of the study endpoint (eg, all-cause mortality).

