5.3.1.3. Clinical outcomes

Measurement	Formula
Incidence of treatment-emergent adjudicated influenza complications	
The incidence of treatment-emergent adjudicated influenza complications from first intake of study drug until the end of the study will be categorized in a hierarchical fashion.
 
The overall category will consist of any complication.
 
The following subcategories are defined:
 
 ▪ Pulmonary complications: 
 • respiratory failure, • primary viral pneumonia, • secondary bacterial pneumonia, • exacerbations of chronic underlying pulmonary diseases, • bronchitis • other complications ▪ Extrapulmonary complications: 
 • Cardiovascular and cerebrovascular disease (eg, myocardial infarction, congestive heart failure, arrhythmia, stroke), • Muscular disorders (eg, myositis, rhabdomyolysis), • Central nervous system (CNS) involvement, • Acute exacerbation of chronic kidney disease, • Severe dehydration, • Decompensation of previously controlled diabetes mellitus, • Other infections (eg, sinusitis, otitis) • Other complications ▪ Pulmonary complications including sinusitis and otitis ▪ Major / minor complications ▪ Infectious / non-infectious complications 
The complications sinusitis and otitis are determined based on their MedDRA preferred terms as listed in Attachment 1, Table 6, for the protocol terms ‘Sinus infection’ and ‘Ear infection’ respectively. Only those terms that are judged to be complications by the adjudication committee will considered for the endpoint ‘pulmonary complications including sinusitis and otitis’.

Incidence of hospital admission 28 days after treatment initiation.	
Was the subject admitted to the hospital? The following medical encounters are considered as indicating hospitalization: ‘Emergency Room’, ‘Intensive Care Unit’, ‘Hospice/Palliative Care Unit’, and ‘Hospital Inpatient Department’. Subjects hospitalized for a preplanned surgery or procedure will not be counted as a hospitalized

	
subject for this endpoint. If a subject is discharged from hospital and subsequently readmitted, the subject will only be counted once as being admitted.
 
Categories will be Yes (1) or No (0).

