
Incidence of treatment-emergent adjudicated influenza complications including hospitalization
	
The incidence of treatment-emergent adjudicated influenza complications from first intake of study drug until the end of the study or hospitalization 28 days after treatment initiation as defined above.
 
Categories will be Yes (1) or No (0).

Time to resolution of fever (hours) [Time-to event]
	
It is assumed that all subjects will have fever at baseline.
 
The time to resolution of fever is defined as the time in hours from initiation of study treatment to the first of a successive series of 3 recordings for which the fever is resolved (see Table 8). The 3 successive recording may have been done over 4 scheduled successive analysis timepoints, in case of 1 missing in between timepoint.
 
In case the resolution of fever is not achieved, data will be censored.
 
Censoring will be done as follows:
 
 1) Last non-missing record(s) indicate resolution of fever (but insufficient recordings to meet the time to resolution) 
Censoring will be done at the first record of resolution of fever from the last series of recordings of resolution of fever
 2) Last non-missing record does not indicate resolution of fever 
Censoring will be done after the last observation, which is 08:00 on the same day if the last observation was a diary entry from 00:01 until 02:00, 20:00 on the same day if the last observation was a diary entry from 02:01 until 14:00, and 08:00 the next day if the last entry was a diary entry from 14:01 until 00:00.
 
Additionally, in the following cases the subject will be censored using a time-to equal to the maximum time across all subjects:
 
 ○ death, ○ if a subject had not resolved the fever at time of hospitalization and/or during hospitalization and no further data on fever resolution is available

Table 8: Resolution criterion for fever

Assessment	Resolution Criterion
Temperature	temperature as recorded on the ePRO device <37.0°C without the use of antipyretics on that day

The following ATC level 4 codes and generic medication names indicate an antipyretic medication:

- N02BA
- N02BE
- Ibuprofen
- Paracetamol
- Acetylsalicylic acid

If an antipyretic medication misses components of its start and/or stop dates (day and/or month and/or year) the following actions will be taken:

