9.2. Pharmacokinetic/Pharmacodynamic Relationships

Pharmacokinetic/Pharmacodynamic relationships will be analyzed for the PD analysis set.

The exposure parameters AUC_{12h} and C_{trough} will be categorized into quartiles for the Day 3 visit, only C_{trough} will be categorized into quartiles for the Day 6 visit. Relationships of these parameters with the primary and selected secondary efficacy endpoints will be explored as follows.

Kaplan-Meier estimates for the time to resolution of the 7 primary influenza-related symptoms will be produced per each quartile for each exposure parameter.

The number and percentage of subjects with treatment-emergent adjudicated influenza complications will be tabulated for each quartile for each exposure parameter.

The number and percentage of subjects admitted to hospital within 28 days after treatment initiation will be tabulated for each quartile for each exposure parameter.

Kaplan-Meier estimates for the time to return to daily activities and for the time to resolution of fever will be produced per each quartile for each exposure parameter.

Relationships of AUC_{12h} with safety will be explored as follows. The number and percentage of subjects with the following treatment-emergent adverse events by AUC_{12h} quartile will be tabulated:

- Any AE
- AEs of worst grade 3 or 4
- Deaths due to AE
- Serious AEs
- AEs for which study drug was permanently stopped
- AEs at least possibly related to study drug
- Confirmed diarrhea events

A cross-tabulation of the worst treatment-emergent toxicity grades versus AUC_{12h} quartile will be presented for the laboratory parameters AST, ALT, and total bilirubin.

Separate tables will be produced for the worst treatment-emergent toxicity grades at Day 3 and overall.

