10.1. Definitions

Measurement	Formula
Number of medical care encounters	Medical care encounters, including surgeries and other selected procedures (inpatient and outpatient), as recorded on the eCRF. The number of medical care encounters is derived as the frequency of the medical encounters other than those mandated in the protocol (eCRF).
Number of outpatient medical care encounters	Similar to the description for number of medical care encounters, but only for outpatient medical care encounters, as recorded on the eCRF (Hospital Outpatient Department, Laboratory Department, Medical Practitioner Office, Home Care).
Frequency of visits of outpatient medical care encounters	Frequency of visits will be provided per outpatient medical encounter type (Hospital Outpatient Department, Laboratory Department, Medical Practitioner Office or Home Care) as reported on the eCRF.
Type of practitioner for hospital outpatient department encounters	Type of practitioner will be provided for Hospital Outpatient Department encounters as reported on the eCRF.

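### The last confirmatory endpoint is called hospital admission, but the SAP lets an emergency room encounter alone count as one

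*SAP*

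**What the plan says.** Protocol 2.1.2 names the secondary endpoint as "The hospital admission rate 28 days after treatment initiation". Protocol 11.4 places "Hospital admission rates 28 days after treatment initiation" third of three in the hierarchy, after time to symptom resolution and influenza complications, and SAP 5.1.1 repeats that order. Neither protocol section says what counts as an admission.

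The operational rule is in SAP 5.3.1.3. The row first asks whether the subject was admitted, and then says: "The following medical encounters are considered as indicating hospitalization: ‘Emergency Room’, ‘Intensive Care Unit", followed by hospice or palliative care and the inpatient department. The only exclusion is a preplanned surgery or procedure, and a readmitted subject counts once. The next row, the composite with complications, uses "hospitalization 28 days after treatment initiation as defined above".

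Elsewhere the SAP describes the result as admission. SAP 9.2 states: "The number and percentage of subjects admitted to hospital within 28 days after treatment initiation will be tabulated".

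**The concern.** Followed literally, the rule scores a subject as admitted on the strength of an ER record. ICU and inpatient encounters have their own entries, so the ER entry can bring in people who were seen and sent home. If the hierarchy reaches this step and succeeds, a superiority statement about hospital admission could rest partly on ER visits.

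The row is also open to two codings. One programmer would take the opening question as governing and another the list of encounter types. That is undesirable for an endpoint under alpha control.

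**Working it through.** The point concerns a definition, so the first check is a comparison of the texts.

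1. **Endpoint name.** Protocol 2.1.2 and 11.4 and SAP 5.1.1 and 9.2 all speak of admission.
2. **Derivation.** SAP 5.3.1.3 makes the encounter type the indicator. Nothing is said about subsequent admission, an overnight stay or a minimum duration.
3. **Other SAP rules that might remove ER-only visits.** SAP 10.1 defines outpatient encounters "but only for outpatient medical care encounters, as recorded on the eCRF (Hospital Outpatient Department, Laboratory Department, Medical Practitioner Office, Home Care"). ER is not among them. SAP 10.2 tabulates encounters by type but does not isolate subjects whose only encounter was in the ER. No other section restricts the ER entry.
4. **Protocol usage in other contexts.** The serious adverse event criterion reads "Requires inpatient hospitalization or prolongation of existing hospitalization". Inclusion criterion 4 reads "Emergency room or hospital observation status for an anticipated duration of <24 hours is not considered hospitalization", provided that no need for hospitalization has been determined. These serve safety reporting and eligibility. They show that the protocol separates the two ideas, but they do not govern the endpoint.

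The plan gives no admission rate, ER rate, effect size or power for this endpoint, so there is no figure to reproduce. The rest is illustration with **assumed** rates, conditional on the test being reached.

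Inputs: n = 300 per arm (the 600 evaluable subjects in Protocol 11.3, randomized 1:1) and two-sided 5%. The counted rate is the admission rate plus the ER-only rate. With p̄ = (p1 + p2)/2:

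- SE0 = √[2p̄(1 − p̄)/n]
- SE1 = √[(p1(1 − p1) + p2(1 − p2))/n]
- power ≈ Φ[(|p1 − p2| − 1.96·SE0)/SE1]

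Results, placebo versus pimodivir:

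- Admissions only, 5% vs 2.5%: (0.025 − 1.96 × 0.01551)/0.01548 = −0.349, power 36%.
- Plus 4% ER-only in both arms, 9% vs 6.5%: (0.025 − 1.96 × 0.02183)/0.02181 = −0.816, power 21%.
- Plus ER-only visits also halved, 9% vs 4.5%: (0.045 − 1.96 × 0.02048)/0.02040 = 0.238, power 59%.

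In the placebo arm of the last two cases, 4/9 = 44% of counted subjects would be ER-only.

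Simulating the SAP's own test gives roughly 30 to 31%, 19% and 57% for the same three cases. That test is Firth logistic regression in each stage with an inverse-normal combination of the one-sided p-values. The simulation used 20,000 trials per case, N1 = 360, 450 or 540, no sample-size increase and no stratum effects. The pattern is the same.

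Range for the dilution case (treatment halves admissions, ER-only visits equal in both arms, simple two-proportion test):

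| Assumed placebo admission rate | ER-only 0% | ER-only 3% | ER-only 6% |
|---|---|---|---|
| 3% | 23.5% | 12.8% | 9.8% |
| 5% | 36.4% | 23.0% | 17.7% |
| 8% | 54.1% | 40.2% | 32.5% |

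**The case against.** **The row opens with an admission question.** The list can be read as the care settings in which an admission is sought. This is a fair reading, but the following sentence lets the encounter type itself stand for hospitalization. At best the row is ambiguous.

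**The choice may be deliberate.** ER is absent from the outpatient types in SAP 10.1, which fits the list in 5.3.1.3. Protocol Section 11 leaves detail to the SAP, and the rule is prespecified and identical in both arms. All of this stands. It answers a charge of invalid inference, but it does not make the endpoint's name describe its content.

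**The ER entry may be needed.** This is the strongest objection. Nothing in the documents shows that a stay beginning in the ER and continuing on a ward produces a separate inpatient or ICU record. If it is entered once, under ER, deleting that entry would lose true admissions. The eCRF is not in the documents, so the number of ER-only visits that would be counted is also unknown. This objection decides the form of the remedy.

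**The consequence is contingent.** The step is reached only after wins on the primary endpoint and on complications. Power moves either way with the assumed rates, so the illustration demonstrates no loss. This is also correct and bears on severity.

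**Conclusion.** The mismatch is real: as written, the last confirmatory endpoint and the composite can count ER visits without admission. It affects what a positive result would mean. Severity is minor to should-fix, and confidence is moderate because the encounter-recording practice is not visible.

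A reader might infer more than the documents support:

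- *That the SAP contradicts the protocol.* It does not, because the protocol has no operational definition and its ER and inpatient wording belongs to other rules.
- *That Type I error is inflated.* It is not, because the test is valid for the endpoint as defined.
- *That the rule favours pimodivir or costs power.* Neither can be said without admission and ER rates, and every rate used above is an assumption.
- *That the ER list also drives hospitalization censoring in the primary endpoint.* SAP 5.2.1 does not define hospitalization or refer to the list, so this is not established.

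**What to change.** **Preferred change, documented as made by blinded sponsor staff.** State in SAP 5.3.1.3 that an ER encounter counts only if it led to admission. Identify such subjects from the recorded encounters together with the item in SAP 7.1.1 that records, for each adverse event, whether hospitalization was required or prolonged. Keep 'Emergency Room' on the list under that condition. Apply the same rule to the composite, and retain the ER-inclusive version as a supportive analysis.

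**Alternative.** The sponsor may prefer not to alter a confirmatory definition after the interim cut of February 28, 2020 (SAP 2.3). It can then keep the rule, label the endpoint as ER visit or hospital admission in the SAP and in reporting, and prespecify an admission-only analysis and a by-arm count of ER-only subjects beside it.

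**Cost.** The first route needs revised wording and one derivation that links encounters to adverse events. It may reduce the event count, and it changes an input to the pre-interim p-value used in the combination test of SAP 5.1.1, so the blinded timing must be on record. The second leaves the confirmatory test untouched. It adds one analysis and one table, but the relabelled endpoint then differs from the protocol's name, and the report should explain this.

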A blinded Adjudication Committee (AC) will be established to adjudicate AEs on predefined criteria for complications (pulmonary versus extrapulmonary, major versus minor, as well as infectious versus non-infectious complications). The AC will receive data on AEs, including medical assessments (eg, chest X-ray results, lab results) and concomitant therapy of cases selected from the AEs. Details will be provided in an AC charter.

- Time to resolution of each of the 10 individual influenza-related symptoms as assessed by the PRO measure Flu-iiQTM. The resolution of each influenza-related symptom is defined as the beginning of the 24-hour period when the influenza symptom score is at most mild or at least back to previous level of symptom severity in case the subject reported the symptom as pre-existing.
- Time to return to daily activities as assessed by the subject.
- Time to resolution of fever. Resolution of fever is defined as a body temperature <37.0°C during a period of 24 hours without the use of antipyretics.
- All-cause mortality.
- PK parameters of pimodivir (ie, plasma concentration just prior to the beginning or at the end of a dosing interval [ $C_{\text{trough}}$ ],  $C_{\text{max}}$ ,  $t_{\text{max}}$ , and  $AUC_{12h}$ ), as determined by population PK analysis.
- The acceptability of the pimodivir formulation in adolescents, as measured by a taste and swallowability questionnaire.
- The emergence of viral resistance against pimodivir detected by genotyping and/or phenotyping.
- Time to viral negativity by qRT-PCR and viral culture.
- Viral load over time by qRT-PCR and viral culture.

Refer to Section 9, Study Evaluations, for evaluations related to endpoints.

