4.6. Prior and Concomitant Medications

Medications reported from 7 days before first dose of study drug and up to last contact date will be summarized by preferred term using the World Health Organization-Drug Dictionary for the ITT-i Set and the Safety Set as frequency tables in 2 parts:

1. Prior medication: medication that started before the first dose of study drug, regardless of when dosing of the medication ended

2. Concomitant medication: medication received at or after the first dose of study drug, medication that was received before initial dosing and continued after initial dosing of study drug, or medication with missing stop date.

(Medication that started before the first dose of study drug and continued after the first dose of study drug will be summarized as prior medication and separately as concomitant medication.)

A frequency tabulation of concomitant medication will be shown by Anatomical Therapeutic Chemical (ATC) class level up to level 3. Frequency tabulations will be made for concomitant antibiotics, type of SOC, corticosteroids, and medication administered to treat COVID-19 infection by ATC class. Additionally, tabulations will be made of concomitant corticosteroids and antibiotics administered because of adverse events reported as influenza complications.

The ATC level 2 code J01 will be used to identify concomitant antibiotics.

The ATC level 2 code H02 and the ATC level 4 codes M01BA, R03BA, and R03AK will be used for identifying corticosteroids.

Separate frequency tabulations will be made for antipyretic medication. The ATC level 3 codes N02BA and N02BE and the generic medication names paracetamol, ibuprofen, and acetylsalicylic acid will be used to identify antipyretic medications.

If a prior/concomitant therapy record misses components of its start and/or stop dates (time and/or day and/or month and/or year), the following actions will be taken:

1. In case of partial start or stop date/times, the concomitant therapy records will be allocated to prior and/or concomitant using the available partial information, without imputations.
2. In case of a completely missing start date, the prior and/or concomitant therapy will be considered as having started before the trial.
3. In case of a completely missing end date, the prior and/or concomitant therapy will be considered as ongoing at the end of the trial.

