1. In case of partial start date

- If the day is missing, then the day will be the first day of the month (or the day of first dose whichever is later)
- If the month is missing the month will be January (or the months of first dose whichever is later)
- If the year is missing, then the year will be the year of first dose

2. In case of partial end date

- If the day is missing, then the day will be the last day of the month (or the day of last contact with the subject whichever is earlier)
- If the month is missing, then the month will be December (or the month of last contact with the subject whichever is earlier)
- If the year is missing, then the year will be the year from the date of last contact with the subject.

3. In case of a completely missing start date, the antipyretic will be considered as having started before the trial

4. In case of a completely missing end date, the antipyretic medication will be considered as ongoing at the end of the trial.

Antipyretic medication use associated with both the morning and evening temperature recordings for a particular day is also obtained

	from the subject's diary. If a subject indicates that they used an antipyretic 'today' then the date of this assessment indicates antipyretic use on that whole day. If a subject indicates that they used an antipyretic 'yesterday' then this indicates antipyretic medication use on the whole day before the assessment day.
Incidence of all-cause mortality	Did the subject die after first dose of study drug? Categories will be Yes (1) or No (0).

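### Fever endpoint: an antipyretic outside the SAP's short coded list goes unflagged when the diary does not report it, so a medicated reading can count as resolution

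*SAP*

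**What the plan says.** Protocol 2.1.2 sets the endpoint: "Resolution of fever is defined as a body temperature <37.0°C during a period of 24 hours without the use of antipyretics". It does not limit which antipyretics count. Protocol Section 8 prohibits no analgesic or NSAID. It requires every therapy to be entered in the eCRF with drug type, treatment period, route and indication.

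SAP 5.3.1.3, Table 8, turns this into a criterion for each reading: "temperature as recorded on the ePRO device <37.0°C without the use of antipyretics on that day". Resolution is dated at the first of three successive qualifying readings; one missing timepoint in between is allowed.

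The SAP then gives two sources for antipyretic use:

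- **Coded medications.** "The following ATC level 4 codes and generic medication names indicate an antipyretic medication": N02BA, N02BE, ibuprofen, paracetamol and acetylsalicylic acid. The list is closed, and no review step is described.
- **Subject diary.** "Antipyretic medication use associated with both the morning and evening temperature recordings for a particular day is also obtained" from the diary. If the subject reports use today, "the date of this assessment indicates antipyretic use on that whole day". If the subject reports use yesterday, "this indicates antipyretic medication use on the whole day before the assessment day". Neither rule is tied to the coded list.

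SAP 4.6 repeats the list for a separate antipyretic table, and "the generic medication names paracetamol, ibuprofen, and acetylsalicylic acid will be used to identify antipyretic medications" alongside the two codes. No diary source is stated there.

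**The concern.** The coded list is narrower than the definition it implements. It names one NSAID, ibuprofen, and so accepts that such drugs can mask fever, but it gives no code for the rest of that class. Two subjects with identical temperatures and nothing in the diary are then treated differently: the ibuprofen user's day is flagged, and the day of a subject on another NSAID is not.

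At stake is the accuracy of one secondary endpoint, which was added on Health Authority feedback (Protocol Amendment 1) and is also analysed by region (SAP 2.3, Table 6). If choice of product differs by country, misclassification could differ between regions. The SAP 4.6 table, which a reader would use to judge antipyretic exposure, would be too low.

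**Working it through.** No sample size, power or event count enters this point, and the plan gives no figure to reproduce. The check is to follow one day with a reading below 37.0°C through SAP 5.3.1.3. I take the two sources as additive, because the SAP says diary use is also obtained.

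| Drug taken that day | Diary reports use | Day flagged | Reading counts towards resolution |
|---|---|---|---|
| On the coded list, recorded in eCRF | Yes or no | Yes | No |
| Not on the list, recorded in eCRF | Yes | Yes, by the diary rule | No |
| Not on the list, recorded in eCRF | No or missing | No | Yes |

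Only the third row departs from the protocol definition.

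**Effect in one affected subject (illustration).** Suppose all readings are below 37.0°C from the morning of Day 3, an unlisted antipyretic is taken on Days 3 and 4 and none from Day 5, and the diary is silent. If the drug is flagged, the first qualifying reading is the Day 5 morning. If it is not, the first is the Day 3 morning. The time is earlier by 2 days × 24 hours = 48 hours. In general, k unflagged days move it by up to k × 24 hours. Because the first qualifying series fixes the event, a later return of fever does not undo it.

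**Number of affected subjects.** This would need the frequency of unlisted use, the proportion not reported in the diary, and the proportion of those users whose readings were low because of the drug. The documents give none of these, nor the wording of the diary question.

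**SAP 4.6.** With no diary source stated, rows two and three are both missed, so the antipyretic table undercounts whether or not the diary works.

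**Label.** SAP 4.6 refers to "The ATC level 3 codes N02BA and N02BE and the generic medication names paracetamol, ibuprofen, and acetylsalicylic acid", whereas 5.3.1.3 calls the same codes level 4. Elsewhere in 4.6, M01BA, a code of the same length, is called level 4.

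**Assumption.** That other NSAIDs and metamizole fall outside N02BA and N02BE is general knowledge of the ATC system. The documents give codes without their contents.

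**The case against.** The strongest reply is that the diary already does this job. It covers morning and evening recordings, flags whole days, reaches back to the previous day, and is not restricted by drug. A reader might infer from the list alone that anyone taking naproxen with a reading of 36.8°C is scored as resolved. That does not follow, because a diary report blocks it. Nor can one assert that subjects fail to recognise such drugs as antipyretics: the diary question may name products or ask about any medicine.

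Other points also carry weight. Protocol Sections 8 and 9.6.4 ask for temperatures to be taken, whenever possible, at least 4 hours after an antipyretic. SAP 4.6 tabulates all concomitant medication by ATC class up to level 3, so use of other NSAIDs will be visible elsewhere. A wider list also has a cost of its own: a flagged day cannot contribute to resolution, and a completely missing stop date is treated as continuing to trial end.

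Most of this stands and narrows the point to the third row of the table. It does not close that row. By keeping a coded list beside the diary, the SAP does not rely on self-report alone, and the coded list is where the gap lies. The 4-hour request is conditional and plays no part in the SAP's criterion. The general medication table does not correct the endpoint.

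**Conclusion.** The point holds in a limited form and is a cheap improvement. A stated rule misclassifies a day when an unlisted antipyretic is in the eCRF but not in the diary, and the SAP 4.6 table will undercount. The conclusion rests on the two sources being additive and on the ATC knowledge noted above.

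Three stronger readings are not supported:

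- **A count of wrong resolution times.** Assuming that 5% to 15% of subjects use an unlisted antipyretic and half do not report it gives 2.5% to 7.5%, or 15 to 45 of the 600 infected subjects in the sample-size section. Both inputs are assumptions. The product counts unreported users, not misdated resolutions, which also need three successive low readings attributable to the drug and no flag by another route.
- **A known direction of bias.** Dilution of a benefit would require that pimodivir shortens fever, that unlisted use follows fever duration, and that diary omission is similar by arm. The documents establish none of these.
- **A threat to the main conclusion.** Time to resolution of fever is outside the confirmatory hierarchy (Protocol 11.4, SAP 5.1.1), so the primary test and type I error are unaffected.

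**What to change.** 1. In SAP 5.3.1.3 and 4.6, extend the list to other systemic antipyretic ingredients: other NSAIDs, pyrazolones, and combination products containing a listed substance.
2. Finalise it before database lock by blinded review of coded concomitant medications by ingredient, route and indication, instead of flagging a whole NSAID class without review.
3. State that a day is flagged if either the coded list or the diary indicates use.
4. Reconcile the ATC level label for N02BA and N02BE between 4.6 and 5.3.1.3.
5. Report the fever result with the current list and with the extended list.

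The cost is SAP wording, a longer code list and one blinded review; the eCRF already collects what is needed. The downside is over-flagging. Subjects record temperature twice daily to Day 14, so someone flagged throughout has none of up to 14 × 2 = 28 readings that can qualify, and is censored. Daily users of an already listed drug are in this position now. A longer list would add chronic users of other drugs and those with a missing stop date, which is why both results should be shown.
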